#### 8.4 ECG Parameters

Electrocardiogram parameters (PR, RR, QRS, QT, QTcF, and QTcB) will be summarized using descriptive statistics for actual values and for change from baseline at each scheduled visit. The minimum post-baseline, maximum post-baseline, and last post-baseline value will be summarized in the same manner, where both scheduled and unscheduled post-baseline measurements will be considered for deriving the minimum/maximum/last post-baseline value.

Note that Frederica's and Bazett's correction to the reported QT interval, QTcF and QTcB, respectively, will be derived (in milliseconds) for all subjects and time points as follows:

QTcF (msec) = 
$$\frac{QT(msec)}{\sqrt[3]{RR(msec)/1000}}$$
; QTcB (msec) =  $\frac{QT(msec)}{\sqrt{RR(msec)/1000}}$ 

The number and percentage of subjects with elevated QTcF and QTcB during the post-baseline period will be presented for the following categories: QTcF or QTcB worsening to >450 msec, >480 msec, and >500 msec from baseline, and increase in QTcF or QTcB from baseline >30 msec and >60 msec.

Overall interpretations of ECG assessment will be tabulated by the number and percentage of subjects in each category (normal, abnormal but not clinically significant, abnormal and clinically significant, not evaluable, or unknown) at each visit and at worst post-baseline assessment.

Electrocardiogram parameters results will also be presented graphically in terms of box plots of absolute values over time and changes from baseline over time.

All ECG measurements and overall interpretation will be listed by subject.

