# 7.4 Safety Analysis

Safety evaluations on the FAS will be based on the incidence, type, severity and consequences (e.g. study discontinuation) of an adverse event (AE) as well as on clinically significant changes in the patient's physical examination, ECGs, vital signs, and clinical laboratory results. ECG parameters will include heart rate (HR), RR interval, PR interval, QRS width and QTc interval. Statistical analysis includes descriptive tabulation using measures which are absolute and relative frequencies for categorical data and means, standard deviations, medians and interquartile ranges for continuous data for observed values as well as for changes from baseline in continuous parameters at each measuring time. Clinical laboratory data, ECGs and vital signs will also be presented graphically in terms of box plots of absolute values over time and changes from baseline over time. Clinical laboratory data will be summarized with respect to the normal ranges of values provided by the laboratory and with respect to predefined levels of change in these values.

All original AE/SAE terms will be coded using the Medical Dictionary for Regulatory Activities (MedDRA). Adverse events will be listed on an individual basis and will be summarized by System organ classes and preferred terms will be used in the analyses. Patients with more than one adverse event within a particular SOC and PT will be counted only once for that SOC and PT. The type and incidence of AEs/SAEs, as well as severity and relatedness to the investigational product will be tabulated.

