#### 3.2 Secondary Study Endpoints

- Standard safety parameters (clinical monitoring, laboratory, and ECG)
- Tolerability and safety of the administration of a diagnostic dose of [Ga]-NeoBOMB1 in patients with malignancies known to overexpress GRPR as determined by absence of:
  - increased number of SAEs compared to other peptide-based radiotracers;
  - clinically relevant changes of physiological parameters (blood pressure, heart rate, and ECG findings)
- Generation of decay corrected tissue time-activity curves (TACs) from [Ga]-NeoBOMB1 PET/CT images in normal organs and tumor lesions.
- Quantification of urinary excretion of [Ga]-NeoBOMB1
- Calculation of half-life of [Ga]-NeoBOMB1 in blood
- Generation of non-decay-corrected TACs from [Ga]-NeoBOMB1 PET/CT images in normal organs and tumor lesions
- Calculation of residence times in critical organs and tumor lesions of [Ga]-NeoBOMB1
- Calculation of absorbed doses in critical organs and effective whole body dose of [Ga]-NeoBOMB1
- Calculation of pharmacokinetic (PK) parameters, such as maximum concentration observed (*Cmax*), time of maximum observed drug concentration occurrence (*tmax*), area under the concentration-time curve from time zero (pre-dose) to some fixed time t [*AUC(o-t)*], AUC(0-t) divided by the dose administered [*AUC(o-t)*/D], half-life (*t*1/2), area under the concentration-time curve from time zero (pre-dose) extrapolated to infinite time [*AUC(o-tinf)*], total systemic clearance for intravenous administration (CL), the apparent volume of distribution of the parent test item in the test system (Vd)
- Number and location of tumor lesion detected by [Ga]-NeoBOMB1 in comparison with comparable standard imaging modalities such as FDG-PET
- Calculation of the [Ga]-NeoBOMB1 PET overall, positive and negative agreement on a lesion-by-lesion basis as well as on a patient basis relative to the standard imaging overall and for each tumor type
- Comparison of number of patients with tumor lesions detected by [Ga]-NeoBOMB1 with cytology and/or histopathology from archival and/or recent biopsy specimens

• Calculation of the [Ga]-NeoBOMB1 PET sensitivity and specificity on a lesion-by-lesion basis for all lesions with associated biopsy data, and on a patient basis relative to histopathology / cytology data

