#### 8.2 Safety Laboratory Parameters

Descriptive statistics will be provided at baseline and each scheduled visit for selected clinical laboratory test results (chemistry, hematology, and coagulation) and changes from baseline to each scheduled visit will be derived. The minimum post-baseline value, maximum post-baseline value, and last post-baseline value will be summarized in the same manner, where both scheduled and unscheduled post-baseline values will be considered for the derivations.

Laboratory values will be assigned toxicity grades when available using the Toxicity Grading Scale in vaccine clinical trials. Directional shifts in laboratory toxicity grades (comparing baseline grade with the worst post-baseline grade) will be analyzed using standard shift tables, presenting number and proportion of subjects and their maximum grade shift. For parameters without a toxicity grading scale, the shift table will present directional shifts from baseline to above or below the laboratory standard normal range using the maximum increase and/or decrease observed throughout the course of treatment/observation. Both scheduled and unscheduled post-baseline values will be considered when deriving the minimum/maximum/worst post-baseline assessment.

Clinical laboratory tests will also be tabulated by the number and percentage of subjects in each abnormal category (abnormal but not clinical significant, abnormal and clinical significant) for each parameter at each scheduled visit and for the worst post-baseline assessment.

Laboratory test results will also be presented graphically in terms of box plots of absolute values over time and changes from baseline over time.

All clinical laboratory data will be listed by subject using the International System of units (SI units). Values outside the normal ranges will be flagged.

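### ECG interpretation is summarised only as marginal counts, so no planned table gives the number of patients whose interpretation worsened from their own baseline

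*SAP*

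**What the plan says.** SAP 3.2 defines tolerability partly by the absence of "clinically relevant changes of physiological parameters (blood pressure, heart rate, and ECG findings". Protocol 7.4 bases the safety evaluation on adverse events and on "clinically significant changes in the patient's physical examination, ECGs, vital signs, and clinical laboratory results". Both are worded as change.

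SAP 8.4 handles ECG data in two ways.

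- **Intervals.** PR, RR, QRS, QT, QTcF and QTcB "will be summarized using descriptive statistics for actual values and for change from baseline at each scheduled visit". Minimum, maximum and last post-baseline values are treated the same way. QTc outliers are counted, including "increase in QTcF or QTcB from baseline >30 msec and >60 msec", and box plots show change over time.
- **Overall interpretation.** "Overall interpretations of ECG assessment will be tabulated by the number and percentage of subjects in each category" (normal; abnormal, not clinically significant; abnormal, clinically significant; not evaluable; unknown), "at each visit and at worst post-baseline assessment". Interpretations are also listed by subject. No cross-tabulation with baseline is specified, and no rule defines a new or worsened interpretation.

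For laboratory data, SAP 8.2 does make that link: "Directional shifts in laboratory toxicity grades (comparing baseline grade with the worst post-baseline grade) will be analyzed using standard shift tables". SAP 5.2 defines baseline as the last assessment before administration begins. SAP 11, which records departures from the protocol analyses, does not discuss the ECG interpretation.

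**The concern.** The overall interpretation is the one ECG variable that carries a judgement of clinical significance, and it can reflect rhythm and ST-T findings that interval statistics do not capture. It is therefore the natural variable for the part of the endpoint about clinically relevant change in ECG findings. A count of patients per category is a marginal distribution. It mixes abnormalities that patients brought into the study with those that appeared after injection.

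Pre-existing abnormality is plausible in this population. No exclusion criterion in protocol 3.4.2 names ECG abnormality, protocol 4.2.1 records hypertension and myocardial infarction as history, and protocol 5.4 permits active systemic anti-cancer treatment. At stake is whether a reader of the summary tables can see how many patients worsened, or must work it out from a listing without a stated rule or denominator.

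**Working it through.** The plan states no figure for this table, so there is none to reproduce. The check is what marginal counts can and cannot determine.

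**Inputs.** N = 50 (SAP 10). Let b be the number abnormal at baseline and w the number abnormal at worst post-baseline. The documents give neither, so both are assumed over a range. All patients are taken to have both readings.

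**Bounds.** The number newly abnormal lies between max(0, w − b) and min(w, N − b).

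| b | w | Lower limit | Upper limit |
|---|---|---|---|
| 5 | 5 | 0 | 5 |
| 10 | 10 | 0 | 10 |
| 15 | 15 | 0 | 15 |
| 20 | 20 | 0 | 20 |
| 5 | 8 | 3 | 8 |
| 10 | 13 | 3 | 13 |
| 15 | 18 | 3 | 18 |
| 20 | 23 | 3 | 23 |

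Take b = w = 10. If the same 10 patients stay abnormal, none is new. If 6 persist and 4 improve, then 10 − 6 = 4 are new. If all 10 improve, 10 of the 40 normal at baseline are new. The planned table is identical in all three cases. The upper limit is a logical extreme: to improve at worst post-baseline, every later reading must be better than baseline. The lower limit is exact only if nobody improves.

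**Unchanged patients in the worst row.** Suppose a proportion p has a clinically significant abnormal ECG at baseline and keeps it. The expected number in the worst post-baseline row with no change is 50p, and one new case makes up 1/(50p + 1) of the row.

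- p = 0.05: 2.5 patients; 1/3.5 = 29%.
- p = 0.10: 5 patients; 1/6 = 17%.
- p = 0.20: 10 patients; 1/11 = 9%.

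These rates are illustrations only.

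**One reading against the worst of several.** Baseline is a single reading. In the dosimetry group, worst post-baseline is the worst of up to six scheduled ECGs: three after injection on Day 1 (protocol 4.1.4), then Days 2, 7 and 14. If each reading of a patient normal at baseline had an independent chance f of being called abnormal with no drug effect, the chance of at least one in k readings is 1 − (1 − f)^k. For k = 6 this is 11.4% at f = 0.02 and 26.5% at f = 0.05 (f assumed). A worst-value comparison therefore leans towards apparent worsening, which is why a shift at each scheduled time is also useful.

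**Whether the baseline margin is visible.** Tabulating by visit should show the screening distribution. Visit 1, however, contains both pre-dose and post-dose ECGs (protocol 4.1.4), and SAP 8.4 does not say that the interpretation table separates them. The baseline reading of SAP 5.2 would normally be the Visit 1 pre-dose ECG.

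**The case against.** A reader might infer that ECG change is not measured at all, or that SAP 8.4 has no link to baseline. The documents do not support that. The same section gives change from baseline for all six interval parameters, including the conduction measures PR and QRS, and counts QTc increases. The missing link concerns the interpretation table only.

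It would also be wrong to say that new findings cannot be identified. Interpretations are listed by subject, and with 50 patients each shift can be read by hand. What is missing is the summary.

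The SAP also follows the letter of protocol 7.4, which asks for frequencies for categorical data and change from baseline for continuous parameters. That stands: this is not a departure from the protocol's stated method. But the same section evaluates safety on clinically significant changes, and marginal frequencies do not count changes.

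The adverse event route is the strongest point on the other side. Protocol 6.1 defines an adverse event as something that emerges or worsens relative to baseline and excludes pre-existing conditions that do not worsen, and SAP 8.1 tabulates treatment-emergent events. A new clinically significant ECG finding may well appear there. It is not assured: protocol 4.1.2 says that abnormal physical-examination findings are recorded as adverse events, while protocol 4.1.4 requires ECG tracings to be reviewed, signed and dated without an equivalent statement.

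A shift table has its own limit. A patient already clinically significant at baseline who develops a different abnormality stays in the same cell. The fix has to allow for this.

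Finally, a reader might extend the point to the laboratory clinical-significance table in SAP 8.2. That is not needed, because 8.2 already plans baseline-to-worst shifts for graded parameters and shifts against the normal range for ungraded ones.

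**Conclusion.** The point holds for the overall ECG interpretation only. The planned table places unchanged pre-dose abnormalities in the worst post-baseline row, and no planned summary gives the number of patients with a new or worsened interpretation. With an assumed 10 of 50 abnormal at both times, 0 to 10 patients could be newly abnormal. The width depends entirely on assumed baseline counts, and rates of 5%, 10% or 20% have no source in the documents. What does not depend on them is that the marginal counts alone do not fix the number of new findings.

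The consequence is limited. The study is descriptive, interval changes are properly summarised, the listing preserves the individual data, and no estimate, error rate or sample size is affected. The change is still worth making: it supplies the within-patient change that the endpoint names, by a method the SAP already uses for laboratory grades.

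**What to change.** In SAP 8.4, add a shift table of baseline interpretation (last pre-dose ECG, as in SAP 5.2) by post-baseline interpretation, at each scheduled time and at worst post-baseline. Show not evaluable and unknown as their own categories so that the rows add up.

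From it, report:

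- the number of patients whose interpretation worsened from baseline;
- within that, the number newly clinically significant, with patients not clinically significant at baseline as the denominator.

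Keep patients already clinically significant at baseline visible in the table and the listing, because the global category cannot show a different new abnormality in them.

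The cost is SAP wording and one extra table. Pre-dose and post-dose ECGs are already scheduled, no procedure changes, and SAP 1 allows revision before database lock. The laboratory tables need no change on this account.

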#### 8.5 Physical Examinations

Physical examination results will be listed by subject.

#### 8.6 Other Safety Parameters

All other variables will be presented in by-subject data listings when data is available.

#### 9 INTERIM ANALYSIS

No formal interim analysis is planned for this study.

#### **10 SAMPLE SIZE AND POWER CONSIDERATIONS**

The primary objective of the trial is to assess preliminary targeting properties of [Ga]-NeoBOMB1. Data for this objective will be reported descriptively therefore no formal statistical sample size calculation is feasible. It is anticipated that 50 patients with malignancies known or suspected to overexpress GRPR will be recruited in the trial and will be administered [Ga]-NeoBOMB1 prior to PET-CT imaging. According to histopathology data, a great percentage of these patients is expected to be GRPR positive. However, some patients will also be recruited whose tumors do not show GRPR positive expression by histopathology/cytology data. This will allow calculation of preliminary diagnostic characteristics and the sample size should allow reasonable precision around estimations of targeting properties. For instance, if a patient level sensitivity of 83.3% is observed (for e.g. if 25 patients had lesions detected by [Ga]-NeoBOMB1 imaging out of 30 patients in the trial with GRPR positive histopathology/cytology) the 95% CI around this would be 66.4% to 92.7%.

The overall sample size of 50 patients will be fixed to ensure 10 patients are recruited within each of the tumor types included in the trial. Although it won't be possible to make strong conclusions within the tumor types, this should ensure that a reasonable number of GRPR positive patients are available within each tumor type and this will allow initial estimates of diagnostic properties to be made and will ensure each tumor type is fairly represented.

Ten patients will be recruited to the dosimetry sub-population of the trial. This is considered sufficient to obtain data on dosimetry, bio-distribution and dose-limiting critical organs. Data from all 50 patients in the trial will be used to assess all other study objectives.

#### 11 CHANGES FROM PROTOCOL-SPECIFIED STATISTICAL ANALYSES

The protocol did not specifically mention that SUVr would be calculated. SUVr will be derived by the statistics group and presented in a data listing.

Since the biopsy data only contains biopsies of one lesion per subject, comparison of the number of tumor lesions detected by [68Ga]-NeoBOMB1 with cytology and/or histopathology from archival and/or recent biopsy specimens will not be performed.
